17.1. Adverse Events

An AE is any untoward medical occurrence, unintended disease or injury, or untoward clinical signs (including abnormal laboratory findings) in subjects whether or not related to the investigational device/procedure.

If a pre-existing condition is present at enrollment, it must be recorded as an adverse event only if the frequency, intensity, or the character of the condition worsens during the study.

For the purposes of this study, all AEs, regardless of relatedness to the study device and/or study device procedure, target limb, or underlying venous disease are **required** to be reported on the AE eCRF and are considered “protocol-reportable”.

All protocol-reportable AEs will be evaluated by the PI using his/her clinical judgement to determine whether the event further meets the criteria for adverse device effect (ADE), serious adverse event (SAE), serious adverse device effect (SADE), or unanticipated adverse device effect (UADE) and will be subject to the respective reporting requirements as outlined in the sections below. The PI or designee is also responsible for informing their IRB/EC of adverse events as required by their IRB/EC reporting requirements and in conformance with FDA and local regulatory reporting requirements. In addition, the PI shall provide documentation of the report submitted to the IRB/EC to Vesper Medical or its designee.

The following types of adverse events must be recorded on the AE eCRF by the PI (or designee):

- Serious Adverse Events
- Any adverse event, regardless of relatedness to the study device, study device procedure, target limb, or underlying venous disease.

The report will include: the AE term, seriousness, severity, action taken, treatment outcome, relationship of the adverse event to the study device and/or study device procedure, and the event status.

All events will be made accessible to the Sponsor and/or designee to review the need for FDA regulatory reporting.

Severity of adverse events will be classified according to the following criteria:

Mild: A mild adverse event is an AE usually transient in nature and generally not interfering with normal activities and not requiring intervention or treatment

Moderate: A moderate adverse event is an AE that is sufficiently discomforting to interfere with normal activities and may require intervention or treatment.

Severe: A severe adverse event is an AE that results in significant symptoms that prevent normal activities and may require hospitalization or invasive intervention.

The relationship of the AE to the device or study device procedure will be classified according to the following criteria:

Unrelated: The AE is clearly not related to the study device or study device procedure.

Possibly: Signs or symptoms of the AE may be related to the study device or study device procedure and/or the natural disease process or other injury/illness.

Definitely: The AE is clearly related to the study device or study device procedure. Signs and symptoms could not reasonably be related to the natural disease process or other injury or illness.

Unknown: Unable to determine the relationship between the study device, study device procedure, natural disease process and/or other injury/illness.

In addition, all AEs will be assessed and recorded in the eCRF by the PI or Sub-I for relatedness to COVID-19 by indicating:

- Yes, related to COVID-19
- No, not related to COVID-19
- Unknown

17.2. Adverse Device Effects

An ADE is defined as any untoward adverse event related to the use of an investigational device or unintended response to a medical device.

Note 1: This definition includes adverse events resulting from insufficient or inadequate Instructions for Use, deployment, implantation, installation, operation, or any malfunction of the investigational medical device (See **Section 18**).

Note 2: This definition includes any event resulting from user error or from intentional misuse of the investigational medical device (See **Section 18**).

A list of events that may be associated with the study device and/or the study device procedure is provided in **Section 16.1**.

17.2.1. ADE Reporting

All ADEs must be evaluated to determine whether the event further meets criteria for a SADE (See **Section 17.5.1**) and would be subject to respective reporting requirements. Non-serious, anticipated ADEs must be reported by the PI (or designee) to the Sponsor and must also be submitted to the IRB/EC per the applicable reporting guidelines. If the event occurred as a result of a device event, respective reporting requirements must be followed as outlined in **Section 18**.

17.3. Serious Adverse Events

A SAE is defined as an adverse event that:

- led to death,
- led to a serious deterioration in the health of the subject, that either resulted in:
 - a life-threatening illness or injury, or
 - resulted in a permanent impairment of a body structure or a body function, or

- required in-patient hospitalization or prolongation of existing hospitalization, or
- resulted in medical or surgical intervention to prevent life-threatening illness or injury or permanent impairment to body structure or a body function, or,
- led to fetal distress, fetal death or a congenital abnormality or birth defect.

Note: Planned hospitalization for a pre-existing condition, or a procedure required by the investigational plan without serious deterioration in health, is not considered a serious adverse event.

For study sites in Germany the following definition of a SAE according to article 3 MPSV (Ordinance on the Medical Device Safety Plan) shall be considered:

A serious adverse event is defined as “any untoward event that occurs during a clinical trial or performance evaluation requiring approval, which has led, could have led or might possibly lead, directly or indirectly, to the death or serious deterioration in the state of health of a subject, user or another person, whether or not the event is related to the medical device” (MPSV § 2 paragraph 5).

17.3.1. SAE Reporting

All SAEs must be evaluated to determine whether the event further meets criteria for a SADE (See **Section 17.5.1**) and would be subject to respective reporting requirements. All events that meet the criteria above for SAEs must be reported by the PI (or designee) to the Sponsor ***within 2 business days (Monday through Friday) from first knowledge of event*** and must also be reported to the IRB/EC per the applicable reporting guidelines.

In Germany, the investigator must report any SAE to the sponsor immediately according to MPSV § 3 paragraphs 4 through 6.

Any SAE with a potentially causal relationship between the event and the investigational medical device or procedures performed as part of the clinical trial or other conditions of the trial conduct will be reported to BfArM immediately. Such related/potentially related SAEs occurring in Germany will be reported via the BfArM SAE report form and on the MEDDEV 2.7.3 table. For all other SAEs, the reports will be submitted quarterly on MEDDEV 2.7.3 table.

SAEs with a causal relationship occurring in other countries will be reported via the MEDDEV 2.7.3 table to BfArM immediately after gaining knowledge and in accordance with the national requirements in the corresponding countries. For all other SAEs, the MEDDEV 2.7.3 table will be submitted quarterly on MEDDEV 2.7.3.

Further, a quarterly evaluation has to be provided to BfArM considering all SAEs occurred in the study. The BfArM template shall be used for this report.

17.4. Major Adverse Events

For this study, the definition of a MAE includes the following events that comprise safety and observational endpoints that require adjudication by the CEC:

- Device or procedure-related death
- Device or procedure-related bleed at the target vessel and/or the target lesion or at the access site requiring surgical or endovascular intervention or blood transfusion of ≥ 2 units
- Device or procedure-related venous injury occurring in the target vessel and/or the target lesion or at the access site requiring surgical or endovascular intervention
- Major amputation of the target limb
- Clinically significant pulmonary embolism, confirmed by CT angiography
- Stent embolization outside of the target vessel
- Presence of new thrombus within the stented segment

17.4.1. MAE Reporting

A major adverse event must be reported by the PI (or designee) to the Sponsor **within 2 business days (Monday through Friday) from first knowledge of event** and must also be reported to the IRB/EC per the applicable reporting guidelines.

17.5. Serious Adverse Device Effects

A SADE is defined as an ADE that results in any of the consequences characteristic of a SAE.

17.5.1. SADE Reporting

All events that meet the criteria above for a SADE must be reported by the PI (or designee) to the Sponsor **within 2 business days (Monday through Friday) from first knowledge of event** and must also be reported to the IRB/EC per the applicable reporting guidelines. If the event occurred as a result of a device event, respective device event reporting requirements must be followed as outlined in **Section 18**.

17.6. Unanticipated Adverse Device Effects

A UADE is defined as any serious adverse effect on health or safety, or any life-threatening problem or death caused by, or associated with, a device, if that effect, problem, or death was not previously identified in nature, severity, or degree of incidence in the investigational plan or application (including a supplementary plan or application), or any other unanticipated serious problem associated with a device that relates to the rights, safety, or welfare of subjects.

17.6.1. UADE Reporting

Any event that is suspected of meeting UADE criteria should be reported in the same manner as a SAE or SADE and must be reported by the PI (or designee) to the Sponsor ***within 2 business days (Monday through Friday) from first knowledge of event*** and must also be reported to the IRB/EC per the applicable reporting guidelines. All SAEs will be reviewed by the Sponsor (or designee) to determine if UADE criteria is met, and if so, the Sponsor or designee will immediately conduct an evaluation and report the results of the evaluation to FDA, all reviewing IRBs/ECs, and participating PIs within 10 business days after the Sponsor first receives notice of the UADE.

17.7. Pregnancies

Female subjects of childbearing potential must use some form of contraception (abstinence is acceptable) throughout the duration of the study. Each pregnancy occurring while the subject is enrolled in the study should be reported to the study Sponsor upon learning of its occurrence. Thereafter, the pregnancy should be followed to determine its outcome.

17.8. Protocol Deviations and Protocol Violations

A protocol deviation occurs when, without significant consequence, the activities on a study diverge from the IRB-approved protocol. Any protocol-required test, assessment, or procedure that is not done or is done out of window is considered a protocol deviation. For example, a subject missing a protocol-required visit due to being away on vacation, or a DUS that is done out of window, would both be considered protocol deviations. All protocol deviations must be documented in EDC and reported to the Sponsor by the PI or designee upon first knowledge of the deviation.

A protocol violation is a divergence from the IRB-approved protocol that may reduce the quality or completeness of data, makes the ICF inaccurate, or impacts a subject's safety, rights, or welfare. Examples of protocol violations include, but are not limited to, the following:

- Inadequate or delinquent informed consent;
- Enrolled subject(s) who did not meet Inclusion/Exclusion criteria;
- Unreported SAEs, UADEs, SADEs;
- Multiple visits missed or visits that took place outside permissible windows;
- Materially inadequate record keeping;
- Intentional deviations from the protocol, GCP, or regulations by study personnel;
- Repeated noncompliance with study requirements;
- Events that may affect the outcome (endpoints) of the study, OR;

- Any other act or occurrence identified by the study Sponsor as constituting a violation from the protocol

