6.3. Observational Endpoints

- Device Success defined as:
 - Successful deployment of the DUO stent(s) at the intended target site, AND
 - Successful withdrawal of the delivery catheter(s) from the introducer sheath, AND
 - The DUO Stent remaining at the intended deployment location through completion of the index procedure as determined by the Principal Investigator (PI)
- Lesion success defined as target lesion patency of $\leq 50\%$ residual diameter or area stenosis of the stented segment at the completion of the procedure*
- Procedural success defined as lesion success without the occurrence of CEC adjudicated major adverse events (MAEs) from the time start of the index procedure through discharge*
- Stent fracture via X-ray through 36 months*
- Stent migration via X-ray through 36 months*
- Stent embolization via X-ray or venogram through 36 months*
- Primary patency of the stented segment via DUS at 24 and 36 months. If DUS shows $>50\%$ stenosis or occlusion, confirmation by diagnostic IVUS may be required.*
- Primary assisted patency of the stented segment via DUS at 24 and 36 months. If DUS shows $>50\%$ stenosis or occlusion, confirmation by diagnostic IVUS may be required.*
- Secondary patency of the stented segment via DUS at 24 and 36 months. If DUS shows $>50\%$ stenosis or occlusion, confirmation by diagnostic IVUS may be required.*
- Changes in the clinical CEAP Classification through 36 months
- Changes in the EQ-5D-3L through 36 months
- Changes in the Villalta Score through 36 months
- Changes in the VCSS Pain Score at 24 and 36 months
- Changes in the VEINES QOL/Sym Score through 36 months
- CEC adjudicated MAEs post 30 days through 36 months
- CEC adjudicated CD-TLR through 36 months
- CEC adjudicated CD-TVR through 36 months
- Venous Ulcer Assessment through 36 months

*Core Laboratory adjudicated

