13.1.3. Baseline Venographic and IVUS Requirements

Baseline venographic and IVUS measurements of the target lesion and target vessels (visual estimate) shall be captured to determine eligibility and include, but are not limited to, the following:

- Target lesion(s) details including vessel location(s), lesion length(s), and pre-PTA % reduction in target vessel lumen diameter
- Indication for stenting and final disease state classification (acute DVT, nonthrombotic, chronic postthrombotic)
- Reference vessel diameter(s)

- Inflow venous patency (if patency of profunda cannot be confirmed by venogram or IVUS, pre-operative DUS findings may be used to confirm)
- Absence of thrombus and/or successfully treated thrombus for acute DVT subjects

13.2. **Pre-Dilation**

Please refer to the Instructions for Use (IFU) for detailed instructions regarding Pre-dilation inflation recommendations. It is recommended that pre-dilation equivalent to the size of the intended stent be performed.

Pre-dilation balloon-related details will be recorded and include, but are not limited to, the following: balloon name/manufacturer and balloon size, max pressure, inflation duration at max pressure, and max inflation diameter across all inflations.

13.3. **Study Device Treatment**

Subjects who meet all inclusion criteria, and who do not meet any exclusion criteria will be deemed eligible for Study Device Treatment.

13.3.1. **Enrollment (Intent-to-Treat)**

A subject is defined as intent-to-treat (ITT) and officially enrolled in the study once the DUO Venous Stent System is advanced through the introducer sheath.

Subjects in whom no DUO Stent implant is placed will be exited after 30 days. Subjects in whom at least one DUO Stent implant is placed will be followed for 36 months.

The per-protocol (PP) population will be defined as ITT subjects with evaluable data that have met the definition for device success, excluding subjects with major deviations, such as those who meet criteria for a protocol violation(s), as determined by the Sponsor.

13.3.2. **Treatment Recommendations**

Please refer to the IFU for detailed instructions regarding recommended criteria for use of the study device and stent sizing. IVUS is required for stent sizing.

NOTE: When overlapping study devices, there should be no more than 2mm of diameter difference between devices.

13.3.3. **Post-Study Device Treatment Measurements**

The following information should be recorded Post-Study Device Treatment:

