19.2. Analysis Groups

A subject is defined as ITT and officially enrolled in the study once the DUO Venous Stent System is advanced through the introducer sheath.

Subjects in whom no DUO Stent implant is placed will be exited after 30 days. Subjects in whom at least one DUO Stent implant is placed will be followed for 36 months.

The full analysis set (FAS) are subjects who meet the ITT definition and have data evaluable for the primary endpoints.

The PP population will be defined as ITT subjects with evaluable data that have met the definition for device success, excluding subjects meeting criteria for a protocol violation(s) as outlined in **Section 17.8** and as determined by the Sponsor.

In addition, a SARS-CoV-2 positive population will be defined as:

1. Any documented confirmation of a SARS-CoV-2 positive test result or SARS-CoV-2 positive antibody test (at any approved testing site) from screening through study exit. Subjects will be grouped according to when they became SARS-CoV-2 positive based on the date that testing was performed as compared to the index procedure (i.e., within 30 days, greater than 30 days but within 12 months, greater than 12 months).
2. In the absence of a SARS-CoV-2 test, subjects will be required to complete a COVID-19 questionnaire. Any subject that completes a questionnaire after screening and answers YES to any question on the questionnaire will be included in the SARS-CoV-2 positive population.
3. Regardless of SARS-CoV-2 status or COVID-19 questionnaire results, all adverse events will be assessed by the PI for relatedness to a possible COVID-19 infection by indicating YES, NO, or UNKNOWN.

Any subject that has an adverse event where the PI indicates YES for relatedness will be included in the SARS-CoV-2 positive group.

Due to the unknown but possible risks associated with COVID-19 and hypercoagulability, once a subject is placed in the SARS-CoV-2 positive population, they will remain there regardless of future SARS-CoV-2 test results and or vaccination status. Any subject not meeting the above criteria will be placed in the SARS-CoV-2 Negative population.

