H₁: Proportion of subjects with freedom from MAE is greater than the (PG) at 30 days, $p_{MAE} > 89\%$

The freedom from MAE proportion will be calculated such that the numerator is the number of subjects in whom a MAE did not occur within 30 days of the index procedure. The denominator is the number of subjects with 30 days of follow-up plus the number of subjects with a MAE prior to 30 days who exited the study prior to 30 days, if any.

Sample Size Rationale: Using PASS 19, a one-sample Exact Test (binomial enumeration), power = 90%, one-sided Type I error controlled at 2.5%, and assumed freedom from MAE of 96.1% with a PG goal of 89%, the required evaluable sample size is 140 subjects.

Primary Statistical Analysis: The primary statistical analysis will be conducted in the FAS subset for the primary safety endpoint overall and in the SARS-CoV-2 negative subset. The primary statistical method is a one-sample exact test comparing the proportion of subjects free from a MAE to the PG using a two-sided $\alpha = 0.05$. The exact two-sided 95% confidence interval for the proportion of subjects free from MAE will be calculated.

The two-sided p-value in the SARS-CoV-2 negative subgroup and all subjects will be calculated and ordered from largest to smallest. If the largest p-value, is statistically significant at $p < 0.05$ then the hypothesis test is statistically significant in both the SARS-CoV-2 negative subset and all subjects. If not, testing continues to the smallest p-value. If the smallest p-value < 0.025 then the hypothesis test is statistically significant in the group for which the smallest p-value is associated with. If the

¹ Razavi MK, Jaff MR, Miller LE. Safety and Effectiveness of Stent Placement for Iliofemoral Venous Outflow Obstruction Systematic Review and Meta-Analysis. Circ Cardiovasc Interv. 2015;8:e002772. DOI: 10.1161/CIRCINTERVENTIONS.115.002772.)

smallest p-value ≥ 0.025 , then the hypothesis test is not statistically significant in either the SARS-CoV-2 negative subset nor all subjects.

Additional Analysis: The evaluation for pooling analyses specified in **Section 19.6** will be completed. If there is missing data for the ITT subjects, the sensitivity to missing data analysis outlined in **Section 19.7** will be completed. Additionally, the primary statistical analysis will be conducted in the per protocol sample overall and in the SARS-CoV-2 negative subset.

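### The supportive per-protocol re-runs use a set whose membership depends on the outcome: procedural stent embolizations drop out by rule, and other exclusions are left to an unblinded sponsor

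*Combined protocol and SAP*

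**What the plan says.** **PP definition.** Section 19.2: "The PP population will be defined as ITT subjects with evaluable data that have met the definition for device success", then "excluding subjects meeting criteria for a protocol violation(s) as outlined in" Section 17.8 and as determined by the sponsor. Sections 13.3.1 and 23 word the exclusion differently: "excluding subjects with major deviations, such as those who meet criteria for a protocol violation(s), as determined by the Sponsor".

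**Device success.** Section 6.3 lists it as an observational endpoint. One of its three conditions is "The DUO Stent remaining at the intended deployment location through completion of the index procedure as determined by the Principal Investigator (PI").

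**Safety endpoint.** Section 6.1 counts stent embolization outside the target vessel as one of seven MAE components.

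**Violations.** Section 17.8 defines a violation as a divergence from the approved protocol with certain consequences. Its examples include serious events that were not reported, "Multiple visits missed or visits that took place outside permissible windows", "Events that may affect the outcome (endpoints) of the study, OR", and "Any other act or occurrence identified by the study Sponsor as constituting a violation from the protocol". The same section gives a duplex scan done out of window as an example of a mere deviation.

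**Use of the PP set.** Under the additional analyses in both 19.10 and 19.11, "the primary statistical analysis will be conducted in the per protocol sample overall and in the SARS-CoV-2 negative subset". Section 19.13 also evaluates safety and efficacy endpoints in PP. The primary tests themselves are run in the FAS (19.10, 19.11), and the success rule in 19.4 does not mention PP.

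**The concern.** A PP analysis is meant to show whether the result holds when treatment was delivered as planned. That works only if subjects are excluded for reasons unrelated to how they fared. Here one entry condition overlaps with a component of the primary safety endpoint. One listed violation, an unreported serious event, can be met only by a subject who had such an event. Two further bullets are broad enough to reach outcomes.

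The sponsor decides, in a single-arm, non-blinded trial (Section 7), and is told of each MAE within two business days (17.4.1). Nothing in the plan requires the PP list to be settled before outcomes are known. The interim-data procedure in 19.5 restricts who sees interim results but does not cover PP classification.

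At stake is what a reader may take from agreement between PP and FAS, and from any PP safety rate that is reported.

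**Working it through.** **1. The overlap, from the text alone.** PP requires device success (13.3.1, 19.2, 23). Device success requires the stent to stay where it was intended through the end of the procedure (6.3). An embolization outside the target vessel during the procedure fails that condition and is an MAE (6.1). Such a subject is a failure in the FAS safety test and absent from the PP one. On this component the PP set can only look better.

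**2. The plan's safety design reproduces.** Inputs from 19.10: performance goal 89%, assumed rate 96.1%, one-sided 2.5%, 140 evaluable. With X ~ Binomial(140, 0.89), the smallest passing count is 132 MAE-free, that is, at most 8 MAEs:
- P(X ≥ 132 | 0.89) = 0.0240
- P(X ≥ 132 | 0.961) = 0.902, against the stated 90%
- 140/(1 − 0.125) = 160 enrolled, as in 19.3

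**3. Illustration of selective removal.** Exact one-sided p-values against 89%, judged at 0.025 and leaving aside the Hochberg step:

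| Set | MAEs / N | MAE-free | p | Result |
|---|---|---|---|---|
| All evaluable | 9/140 | 93.6% | 0.048 | fails |
| One MAE subject removed | 8/139 | 94.2% | 0.0255 | just fails |
| Two MAE subjects removed | 7/138 | 94.9% | 0.012 | passes |
| Two MAE and 10 MAE-free removed | 7/128 | 94.5% | 0.0239 | passes |
| Two MAE and 11 MAE-free removed | 7/127 | 94.5% | 0.0255 | fails |

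The reversal needs two MAE subjects removed and no more than 10 MAE-free subjects lost with them.

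**4. Error of the PP re-run taken alone.** The documents give no exclusion rate. Assume a share q of failures is dropped and no successes are, with the truth at the performance goal:

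| q | PP safety, N=140 | PP efficacy, N=128 (range over the ten disease mixes in the 19.11 table) |
|---|---|---|
| 0 | 0.024 | 0.019–0.028 |
| 10% | 0.034 | 0.062–0.072 |
| 20% | 0.070 | 0.154–0.176 |

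The safety column is exact. The efficacy column simulates the 19.11 Z-test with its null variance, 200,000 runs per mix. For efficacy, q above zero requires the sponsor to use its discretion that way; the text does not compel it.

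**5. Out-of-window visits.** One sentence of 17.8 makes a late duplex scan a deviation (kept in PP). A bullet in the same section makes out-of-window visits a violation (dropped), unless its opening word is read to govern both halves. Under 19.11, an assessment after the window can only declare a subject patent; lack of patency needs a reintervention or a non-patent assessment in the window. Dropping late-scan subjects therefore removes successes.

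**The case against.** The strongest reply is that no decision rests on PP. Both primary tests use the FAS, 19.4 defines success without PP, 19.7 adds best-case, worst-case and tipping-point analyses in ITT, and 19.13 reports ITT beside PP. This stands. A reader might infer that the trial's Type I error is inflated or that a failed trial could be rescued; the documents do not support either.

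A reader might also infer that patency failures are removed by rule. They are not. The bullet on events affecting endpoints sits under a definition that requires a divergence from the protocol, and an MAE or loss of patency is not in itself a divergence. That narrows the bullet but does not close the gap: the catch-all is open-ended, and an unreported serious event is a true divergence that depends on the subject having had the event.

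The automatic overlap is one of seven MAE components, and only when it occurs during the procedure. Bleeding, pulmonary embolism, amputation or new in-stent thrombus does not by itself fail device success. Requiring device success for an as-planned efficacy set is arguable design; it is harder to defend for a safety analysis.

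Finally, it is tempting to read the out-of-window wording as favouring the device. Under 19.11 it works the other way, so it is an ambiguity and not a bias toward success. The two-subject reversal is likewise a constructed case: it assumes exactly 9 MAEs and, as shown, disappears if 11 MAE-free subjects are also excluded.

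**Conclusion.** The point holds in a limited form. The PP set depends on the outcome by rule for procedural stent embolization, and by unblinded sponsor discretion through the 17.8 list. Agreement between PP and FAS is therefore not reliable corroboration, and PP safety can only favour the device on the embolization component. The primary conclusions and their formal error rate are untouched.

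The size cannot be fixed from the documents, which give neither a rate of procedural embolization nor a rate of PP exclusion. The move from p=0.048 to p=0.012 assumes 9 MAEs in 140, two removed, and every MAE-free subject kept. The error rates assume that only failures are dropped. Both show sensitivity; neither is a forecast. The change is worth making because it is cheap and removes an exclusion tied to the endpoint.

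**What to change.** Amend Sections 13.3.1, 19.2 and 23, and the use of 17.8 for PP:

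(a) Do not apply device success or violation exclusions to safety. Report safety in ITT/FAS only.

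(b) Define PP efficacy by a closed list: consent or eligibility failure, no DUO Stent placed, and no determinable 12-month endpoint status under 19.11. The last criterion should not be worded as missing 12-month imaging: 19.11 counts a qualifying reintervention before the window closes as lack of patency, and a subject with one must stay in as a failure even without a later scan. Do not use the bullets on endpoint-affecting events, unreported serious events or the sponsor catch-all as PP criteria.

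(c) Reconcile the two out-of-window statements in 17.8, and bring the PP wording in 13.3.1 and 23 into line with 19.2.

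(d) Fix the PP list before adjudicated outcomes are released to those deciding it, and report each exclusion with its reason and the subject's endpoint status.

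The cost is protocol and SAP wording. The sponsor loses discretion over PP membership, and PP results may look slightly less favourable.
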